7.2 Statistical Methods

We have a dedicated statistician for this clinical trial ([name], PhD). Our inclusion criteria use a baseline SD of systolic blood pressure variability ≥15 mmHg (2 SD above our age-matched control data [8.7±3 mmHg]). The mean coefficient of variation in 24-h BP readings in patients with FD is 19.1±5 and 99% of FD patients meet the inclusion criteria. Preliminary data shows that treatment with high dose carbidopa (600 mg/day) reduces blood pressure variability (SD of daytime SBP) by 7.0±5.5 mmHg. Power analysis for the primary outcome (reduction in SD of daytime SBP variability) is detailed in table 3. A sample size of 20 achieves 80% power to detect a reduction of 2.5 (or 2.9) from the null hypothesis of no reduction with an estimated standard deviation of 4.4 for the difference in SD at a significance level of 0.05 using a one-sided (or two-sided) one-sample t-test. The minimum detectable differences are all well below the observed reduction of BP fluctuation of 5.1 from our preliminary data. To ensure that the study is well powered, we will choose a sample size of 30 patients. To account for a drop out rate of around 15%, we will enroll 36 patients in the trial. We will examine the sample distribution of SD of daytime SBP, and if it deviates from the normal distribution, we will employ the nonparametric Wilcoxon test for robustness. In addition, to account for potential covariates, such as age, gender, and disease severity, the analysis of (co)variance (ANOVA and ANCOVA) methods will be used to model the repeated measures data.

Table 3: Power Calculation and Sample Size

Minimal detectable difference: SD BP variability high vs. low dose							
Sample size	T-test	T-test					
	One-sided	Two-sided					
20	-2.5	-2.9					
30	-2.0	-2.3					
40	-1.8	-2.0					

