A data and safety monitoring board (DSMB, Chaired by [name]) will review safety data on an ongoing basis. The study will continue until the target number of patients is enrolled or the DSMB recommends stopping the trial. To allow for a flexible trial design, there will be an interim efficacy analysis with access to the un-blinded after the first 15 patients have completed the trial. If carbidopa is found to significantly reduce blood pressure variability and the 300 mg/day (low-dose) is found to be equivalently effective as the 600mg/day (high-dose), we will decide, with the DSMB, whether to amend the protocol to add an additional treatment arm to test doses lower than 300 mg/day. Alternatively, if there is insufficient evidence to suggest that 600 mg/day of carbidopa reduces blood pressure variability, before terminating the trial for futility, we will drop the ineffective arms and collect exploratory data to explore the effectiveness of higher carbidopa doses up to 900 mg/day (for 28 days). We will modify the trial to include a titration from upwards of 600 mg/day in increments of 50 mg/day increases per week. To monitor safety closely, we will collect additional safety bloods (CBC and metabolic panel), 12 lead ECG and conduct comprehensive neurological examinations with each incremental titration step up and patients will be contacted by interim phone-calls to monitor adverse events. Only patients that live within 2-hours of the Dysautonomia Center will be included in the subsection to explore the efficacy of higher carbidopa dosages. We will conduct new power analyzes with the accumulated data and revise the sample size accordingly. Final analysis will be performed after the final study patient has completed the trial and the study is closed for enrollment. All end-points will be first examined using descriptive statistics. Each patient will serve as their own control allowing paired comparisons to be made between high-dose, low-dose and placebo data.

9 Data Handling and Record Keeping

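### Sample size may be revised after an unblinded interim efficacy look, and no named analysis is adjusted for it, so control of type I error at 0.05 is not assured

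*Combined protocol and SAP*

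**What the plan says.** - **Interim look.** Section 8.6.1: "there will be an interim efficacy analysis with access to the un-blinded after the first 15 patients have completed the trial". The look compares carbidopa with placebo and low dose with high dose. It can lead to an added arm, or to dropped arms and exploration of higher doses.
- **Trigger.** One branch opens with "If carbidopa is found to significantly reduce blood pressure variability". No interim significance level is given, and section 8.5 states that there are no specific stopping rules.
- **Revision of N.** Section 8.6.1, after the sentences on the higher-dose part: "We will conduct new power analyzes with the accumulated data and revise the sample size accordingly". No rule, minimum, maximum, driving contrast or scope follows.
- **Analyses.** The t-test appears in the power calculation of section 7.2, "at a significance level of 0.05 using a one-sided (or two-sided) one-sample t-test". That section also names a Wilcoxon test if normality fails, and ANOVA/ANCOVA for the repeated measures. Section 8.6.1 adds paired comparisons among high dose, low dose and placebo. None of these separates patients before and after the interim or changes a critical value.
- **Planned size.** Section 7.2: "we will choose a sample size of 30 patients", then "To account for a drop out rate of around 15%, we will enroll 36 patients in the trial".

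**The concern.** A fixed-sample test keeps its level if N does not depend on the effect seen so far. If a weak interim effect leads to a larger N and a strong one to a smaller N, the pooled statistic no longer has its nominal null distribution. The revision sentence comes in the same section as an unblinded efficacy look, so re-powering on the observed effect is a natural reading and nothing in the plan excludes it.

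This is separate from the missing interim thresholds. Writing a significance or futility cut-off would not repair a pooled test whose N had been tuned to the effect.

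What is at stake is mainly 300 mg versus placebo and 600 versus 300 mg. The dose comparison is Aim 3, and section 1.5 says it will inform the choice of doses for a phase III trial. A nominal p below 0.05 there could overstate the evidence.

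**Working it through.** **1. The plan's own figures.** Inputs from section 7.2: SD of the within-patient difference 4.4, alpha 0.05, power 80%. Solving the exact noncentral t for the detectable difference gives:

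| n | One-sided, recomputed (Table 3) | Two-sided, recomputed (Table 3) |
|---|---|---|
| 20 | 2.54 (2.5) | 2.91 (2.9) |
| 30 | 2.05 (2.0) | 2.33 (2.3) |
| 40 | 1.76 (1.8) | 2.00 (2.0) |

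Enrolment: 30/(1 − 0.15) = 35.3, rounded up to 36. The plan's figures reproduce, and with N fixed at 30 the test has its nominal level.

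**2. Assumed revision rule.** The plan gives none, so these are assumptions: interim at n = 15; d and s are the interim mean and SD of the within-patient difference for one contrast; two-sided 0.05; 80% power;

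N = (1.96 + 0.842)² × (s/d)² = 7.85 × (s/d)², rounded up and held within limits.

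Two illustrations with s = 4.4:
- d = 2.33 gives 7.85 × (4.4/2.33)² = 28.0, held at a floor of 30.
- d = 1.6 gives 7.85 × (4.4/1.6)² = 59.4, so N = 60.

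N therefore moves with the observed effect.

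**3. Type I error when N is tuned to the tested contrast.** Simulation with no true effect, real t-tests and at least 150,000 trials per rule. The combination test is Z = (z₁ + z₂)/√2, where z₁ and z₂ come from the one-sided p-values of the first 15 and the later patients.

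| Limits on N | Unadjusted pooled test | Combination test |
|---|---|---|
| 30 to 60 | about 6.0% | about 5% |
| 20 to 60 | about 6.8% | about 5% |
| 20 to 100 | about 7.4% | about 5% |

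Across separate runs the combination test gave 4.9% to 5.2%.

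**4. Rules that add little or nothing.**
- *SD only:* N from s and a fixed target difference, never below 30: 5.1% to 5.3%. If N may fall to 18: 5.7% to 5.8%.
- *Conditional-power zone:* N raised only when conditional power at N = 30 is at least 0.5 and below 0.8, maximum 60 or 90: 4.9% at one-sided 0.05.
- *N driven by 600 mg versus placebo, after a significant interim for it:* three arms with independent, equal-variance errors giving SD 4.4 for differences, true 600 mg effect 5.1, no 300 mg effect. Error for 300 mg versus placebo is 4.95% (N 30 to 60) and 4.8% (N 20 to 60). With both doses truly at 5.1, error for 600 versus 300 mg is 4.7% and 4.8%.

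**5. What causes the inflation.** In the same gated three-arm setting, re-powering on the tested contrast itself brings the error back to about 5.9% (N 30 to 60) and 6.6% to 6.7% (N 20 to 60). A contrast that merely continues whatever its interim result was is not inflated. Tuning N to that contrast is what inflates it.

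**6. Price of the combination test.** At N = 30 and a true difference of 2.33 (SD 4.4), power is 79.4%, against 80.1% for the pooled t-test: 80.1 − 79.4 = 0.7 points.

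**The case against.** The strongest reply is that the plan speaks of accumulated data, not of the observed effect. Revision from the SD alone fits those words and adds almost nothing to the error. The sentence also follows directly on the exploratory higher-dose text, so it may cover only that modified part and leave the main comparison at its planned size. If 600 mg versus placebo drives N behind a significance gate, the other two contrasts stay at about 5%. Even on the unfavourable reading with N only rising, the excess is about one percentage point, in a single-centre phase 2 trial whose dose comparison is described as preliminary.

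All of this stands, and it rules out several stronger statements that a reader might infer:

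- *The false-positive rate exceeds 0.05.* The documents do not give the rule that would decide this.
- *An ordinary t-test is the only stated final test.* Section 7.2 names it in the power calculation and also names Wilcoxon and ANOVA/ANCOVA. The accurate point is that none of them is adjusted.
- *The 300 mg and dose contrasts are inflated because they continue regardless of their own interim result.* Step 5 shows that this is not the mechanism.
- *The error could be about 10%.* That figure needs N to be chosen in the most favourable way within 15 to 60. The plan ties the revision to power analyses, so this is an adversarial bound and not a realistic reading.

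The reply does not show that error is controlled. Whether it is 5% or 7% rests on a rule that could be chosen after unblinding.

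**Conclusion.** The point holds as a gap in error control, not as a demonstrated excess. The plan allows an unblinded efficacy look followed by an unspecified revision of N, and none of its named analyses allows for this. Under assumed rules that re-power on the tested contrast's own observed effect, two-sided error is about 6.0% to 7.4%, depending on the limits on N. Under the other plausible rules in step 4 that keep N at 30 or more, it stays near 5%. These figures rest on an interim at exactly 15, normally distributed differences, 80% target power and limits on N that the plan does not state. The inflation is modest and the remedy is cheap, so the plan should be changed, but the design itself is not invalid.

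**What to change.** In sections 8.6.1 and 7.2, state:

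1. whether the revision covers the main 600 mg, 300 mg and placebo comparison or only the modified higher-dose part;
2. which contrast drives N, and the minimum and maximum N.

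Then adopt one of two rules before any unblinding:

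- **(a) SD-only revision.** Recalculate N from the SD of the within-patient differences for a pre-set target difference, with N never below 30. Control is approximate (about 5.1% to 5.3%). The sponsor gives up re-powering on the observed effect.
- **(b) Combination test.** Keep the unblinded revision, but test each continuing contrast with an inverse-normal combination of the p-values from the first 15 patients and from the later patients, with equal weights fixed in advance. Simulated error is about 5%. If N stays at 30, power is about 79.4% instead of 80.1%.

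Either way the cost is SAP wording, plus a short addition to the analysis code under (b). The text is best written together with the interim thresholds that section 8.6.1 also lacks.

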9.1 Confidentiality

Study subjects will be given a unique ID code, data will be maintained on password protected computers and subject charts will be stored in locked offices in locked cabinets.

9.2 Confidentiality and HIPAA

Information about study subjects will be kept confidential and managed according to the requirements of the Health Insurance Portability and Accountability Act of 1996 (HIPAA). Those regulations require a signed subject authorization informing the subject of the following:

- What protected health information (PHI) will be collected from subjects in this study
- Who will have access to that information and why
- Who will use or disclose that information
- The rights of a research subject to revoke their authorization for use of their PHI.

In the event that a subject revokes authorization to collect or use PHI, the investigator, by regulation, retains the ability to use all information collected prior to the revocation of subject authorization. For subjects that have revoked authorization to collect or use PHI, attempts should be made to obtain permission to collect at least vital status (i.e. that the subject is alive) at the end of their scheduled study period.

9.3 Source Documents

Source data is all information, original records of clinical findings, observations, or other activities in a clinical trial necessary for the reconstruction and evaluation of the trial. Source data are contained in source documents. Examples of these original documents, and data records include: hospital records, clinical and office charts, laboratory notes, memoranda, subjects' diaries or evaluation checklists,

pharmacy dispensing records, recorded data from automated instruments, copies or transcriptions certified after verification as being accurate and complete, microfiches, photographic negatives, microfilm or magnetic media, x-rays, subject files, and records kept at the pharmacy, at the laboratories, and at medico-technical departments involved in the clinical trial.

9.4 Case Report Forms

The study case report form (CRF) is the primary data collection instrument for the study. All data requested on the CRF must be recorded. All missing data must be explained. If a space on the CRF is left blank because the procedure was not done or the question was not asked, write "N/D". If the item is not applicable to the individual case, write "N/A". All entries should be printed legibly in black ink. If any entry error has been made, to correct such an error, draw a single straight line through the incorrect entry and enter the correct data above it. All such changes must be initialed and dated. DO NOT ERASE OR WHITE OUT ERRORS. For clarification of illegible or uncertain entries, print the clarification above the item, then initial and date it.

9.5 Records Retention

Study documents will be maintained indifiently.

10 Study Monitoring, Auditing, and Inspecting

10.1 Study Monitoring Plan

The investigator will allocate adequate time for such monitoring activities. The Investigator will also ensure that the monitor or other compliance or quality assurance reviewer is given access to all the above noted study-related documents and study related facilities (e.g. pharmacy, diagnostic laboratory, etc.), and has adequate space to conduct the monitoring visit.

10.2 Auditing and Inspecting

The investigator will permit study-related monitoring, audits, and inspections by the IRB/EC, the sponsor, government regulatory bodies, and University compliance and quality assurance groups of all study related documents (e.g. source documents, regulatory documents, data collection instruments, study data etc.). The investigator will ensure the capability for inspections of applicable study-related facilities (e.g. pharmacy, diagnostic laboratory, etc.).

Participation as an investigator in this study implies acceptance of potential inspection by government regulatory authorities and applicable University compliance and quality assurance offices.

11 Ethical Considerations

This study is to be conducted accordance with applicable US government regulations and international standards of Good Clinical Practice, and applicable institutional research policies and procedures.

This protocol and any amendments will be submitted to a properly constituted Institutional Review Board (IRB) or independent Ethics Committee (EC) in agreement with local legal prescriptions, for formal approval of the study conduct. The decision of the IRB/EC concerning the conduct of the study will be made in writing to the investigator and a copy of this decision will be provided to the sponsor before commencement of this study. The investigator should provide a list of IRB/EC members and their affiliate to the sponsor.

All subjects for this study will be provided a consent form describing this study and providing sufficient information for subjects to make an informed decision about their participation in this study. This consent form will be submitted with the protocol for review and approval by the IRB/EC for the study. The formal

consent of a subject, using the IRB/EC-approved consent form, must be obtained before that subject undergoes any study procedure. The consent form must be signed by the subject or legally acceptable surrogate, and the investigator-designated research professional obtaining the consent.

In addition, describe who will obtain consent and how the process of informed consent will be structured to be conducive to rational and thoughtful decision making by the subject/subject's legally authorized representative. If children and/ or cognitively impaired adults will be subjects, include a specific plan to assess comprehension during assent or the subject's agreement Individuals who are authorized to obtain consent must be listed on the protocol (or FDA form 1572) and consent form document. If necessary to use 'Auditor/Witness' and/or translator, these roles would be described in this section.

Include a plan for assessing subject capacity in cognitively impaired subjects. Describe the anticipated degree of impairment relative to their ability to consent and the anticipated direct benefits to the subjects.

12 Study Finances

12.1 Funding Source

This study is being funded by a grant from the Food and Drug Administration.

12.2 Conflict of Interest

Any investigator who has a conflict of interest with this study (patent ownership, royalties, or financial gain greater than the minimum allowable by their institution, etc.) must have the conflict reviewed by a properly constituted Conflict of Interest Committee with a Committee-sanctioned conflict management plan that has been reviewed and approved by the study sponsor prior to participation in this study. All NYULMC investigators will follow the applicable University conflict of interest policies.

Appendix:

ORTHSTATIC HYPOTENSION QUESTIONNAIRE

We are interested in measuring the symptoms that occur because of your problem with low blood pressure (orthostatic hypotension) and the degree that those symptoms may interfere with your daily activity. It is important that we measure the symptoms that are due ONLY to your low blood pressure, and not something else (like diabetes or Parkinson's disease). Many people know which of their symptoms are due to low blood pressure. Some people who have recently developed problems with low blood pressure may not easily distinguish symptoms of low blood pressure from symptoms caused by other conditions. In general, symptoms of your low blood pressure problem will appear either upon standing or after you have been standing for some time, and will usually improve if you sit down or lie down. Some patients even have symptoms when they are sitting which might improve after lying down. Some people have symptoms that improve only after sitting or lying down for quite some time.

Please answer the next questions keeping in mind that we want to know only about those symptoms that are from your problem with low blood pressure.

OH SY	OH SYMPTOM ASSESSMENT (OHSA)											
Please tick the number on the scale that best rates how severe your symptoms from low blood pressure have been on the average over the past week. You should respond to every symptom. If you do not experience the symptom, circle zero (0). YOU SHOULD RATE ONLY THE SYMPTOMS THAT ARE DUE TO YOUR LOW BLOOD PRESSURE PROBLEM. 1. Dizziness, lightheadedness, feeling faint, or feeling like you might black out												
None	0	1	2	3	4	5	6	7	8 90 u	9	10	Worst
												possible
2. Probl	ems w	ith vis	ion (bl	urring	, seeiı	ng spo	ts, tur	nel vi	sion, e	etc.)		
None	0	1	2 □	3	4	5	6	7	8	9	10	Worst possible
3. Weak	ness											
None	0	- □	2 □	3	4	5	6 🗌	7	∞ 🗌	9 🗆	10	Worst possible
4. Fatigi	ue											
None	0	1 □	2 □	3	4	5	6 🗌	7	∞ 🗌	9	10	Worst possible
5. Trouble concentrating												
None	0	-□	2	ვ □	4	5 🗌	6 🗌	7	∞ □	 	10	Worst possible
6. Head	6. Head and neck discomfort											

CARBIDOPA IN FAMILIAL DYSAUTONOMIA PHASE II STUDY

Page 31

Version: 5.0 (date February 12, 2018)

None	0	1	2	3	4	5	6	7	8	9	10	Worst
												possible

OH DAILY ACTIVITY SCALE (OHDAS)									
We are interested in how the low blood pressure symptoms that you experiences affect daily life. Please rate each item by ticking the number that best represents how much on the average the activity has been interfered with over the past week by the low blood pressure symptoms you have experienced. If you cannot do the activity for reasons other than low blood pressure, please check the box at right.									
			☐ Cannot do for other						
1. Activities that red	quire standing f	or a short time	reasons						
No 0	No 0 1 2 3 4 5 6 7 8 9 10 Complete								
interference			│						
	☐ Cannot do for other								
2. Activities that red	quire standing for	or a long time	2. Activities that require standing for a long time reasons						
	1 2 3								
	1 2 3								
No 0	1 2 3		9 10 Complete						
No 0 interference	1 2 3		9 10 Complete						
No 0 interference		4 5 6 7 8	9 10 Complete interference						
No 0 interference		4 5 6 7 8	9 10 Complete interference Cannot do for other reasons						
No 0 interference 3. Activities that red	quire walking fo	r a short time	9 10 Complete interference Cannot do for other reasons						
No 0 interference 3. Activities that rec	quire walking fo	r a short time	9 10 Complete interference Cannot do for other reasons 9 10 Complete						
No 0 interference 3. Activities that rec	quire walking fo	r a short time	9 10 Complete interference Cannot do for other reasons 9 10 Complete						
No 0 interference 3. Activities that rec	quire walking fo	r a short time 4	9 10 Complete interference Cannot do for other reasons 9 10 Complete interference						
No 0 interference	quire walking fo	r a short time 4	9 10 Complete interference Cannot do for other reasons 9 10 Complete interference Cannot do for other						

SYMPTOM DIAR	Y					
Name (last, first	t):					
Current dat	-		Time:			
Retching is the effor Please mark the bo Please make only o	x in each rov	w that most o		ponds to you	ır experience	-
In the last 24 hours, I have felt nauseated or sick to my stomach	Not at all	1-hour or less	2-3 hours	4-6 hours	More than 6 hours	
In the last 24 hours, from nausea/sickness, I have felt "" distress	No	Mild	Moderate	Great	Severe	
In the last 24 hours, I have had periods of retching.	No	1 – 2 hours	3 – 4 hours	5 – 6 hours	7 or more	
What time of day was the worst?						
Did you miss school or work?	□ No □ Yes					
Did you take something for your nausea today?	□ No □ Yes	 3				
Did you take something for your blood pressure today?	□ No □ Yes					
Did you have anything else that bothered you today (an Adverse Event)?						

Diary Day: 1 of 28

Sample Instructions for Testing/Dose administration:

Dov	Instructions
Day	Instructions
Apr 1st The day before your visit	At 9 AM fit the BP cuff to your < <left>> arm (<<6>> cm above your elbow). Turn the monitor on, start the recording by pressing the blue button, go about your daily activities. Fill in the diary your meal times, times you took medications and the time you go to sleep and wake up. Starting this same morning, discard your first morning urine. For the next 24-h collect your urine in the container provided. Write here when you started the collection. START TIME: AM You should continue to take your study medication every 6-hours.</left>
Apr 2nd The day of your visit	Your appointment or televisit at the Dysautonomia Clinic is scheduled for <<10:00>> AM. Finish your urine collection the same time you started it the previous day. Be sure this time to include your first early morning urine sample after waking up. Write here when you ended the collection: END TIME: AM Take your first morning dose of study medication at <<8:00>> AM. Write down here the exact time you took your medication. MEDICATION TIMING: AM Come into the clinic for your study visit. At 11 AM we will perform your autonomic function tests in the office of via telemedicine. DO NOT take off your BP monitor yet, will take it off when you arrive at the clinic. Here is a check list with things to bring with you to the clinic or have prepared for the televisit: Your symptom diary Your 24-h urine collection The blood pressure monitor (which you should be still wearing) All your unused medication After your visit: So that you do not stop your dose too quickly, we will reduce your current dose slowly. At the end of this visit, we will give you 2 bottles of medication. One bottle will be marked with todays and tomorrows dates, and will contain 2 of the same pills that you have been taking. One bottle will contain more pills. These pills are your next treatment, and you should not start taking them yet. You will take one-pill from the bottle with today and tomorrows date. Once you have taken this pill, do not take any more pills for the rest of the day.
Apr 3rd The day after your visit	IN THE AFTERNOON, TAKE ONE PILL FROM THE BOTTLE MARKED WITH TODAY'S DATE. Do not take any more medication for the rest of the day Apr 2: Take 1 pill Apr 3: Take 1

Apr 4th Washout No pills	DO NOT TAKE ANY MEDICATION TODAY
Apr 5th Washout No pills	DO NOT TAKE ANY MEDICATION TODAY
Apr 6th Start your new medications today	Start taking your next batch of study pill again, three times a day (every six hours) Morning dose: 8:00 AM Afternoon dose: 2:00 PM Evening dose: 8:00 PM Be sure to keep your diary with your symptoms We will call you in the morning at 10:00 AM to check how you responded to
1000	your first dose of new medication. If you do not feel well, we will ask you to come into the Center.
Apr 7th Continue your three a day schedule	Take your study pills three times daily until May 4th, when you come to the Clinic. Remember to fill your diary
Apr 12th Phone call Safety bloods	We will contact you by phone to check in on how you are feeling. We will arrange for you to have a blood test to check your health status.
May 3rd Day before next visit	Repeat ambulatory monitoring and urine collection. We will send you new instructions with dates and times.
May 4th Next visit # X	Plan to attend your next study visit at the clinic

If you feel unwell at any time, call the Dysautonomia Center at: [contact].

AMBULATORY
MONITORING:
INSTRUCTIONS FOR
PATIENTS

https://dysautonomia.nyumc.org [contact]

You have been asked to wear an ambulatory blood pressure monitor. This will measure your blood pressure for 24-h so that we can better understand of how it changes over a typical day. Some patients may need to wear the monitor for longer.

Step 1: Fitting the cuff

- Place the cuff on your non-dominant arm (the one you don't write with). So it does not restrict movement, it should be on your upper arm, completely above the elbow. The cuff should be tight enough to not fall down, but not uncomfortable. The orange tubing needs to face UP. The word "ART" and arrow should on the inside of your elbow.
- The monitor itself can be worn on a belt or carried in a bag. Make sure you do not drop it.

3.

- Turn the monitor on by flipping the black switch from OFF (O) to ON (I). You should see numbers or letters on the display screen when the monitor is initially on.
- Once the monitor is on press the BLUE button to start the readings.
- The cuff will inflate and start taking your blood pressure

Step 3: Measuring your blood pressure

- The cuff will inflate every 30 minutes to take your blood pressure. The screen may not show your blood pressure readings. The monitor will store your readings in its internal memory.
- When the cuff is inflating, make certain you keep you arm relaxed and still. If the machine cannot measure your blood pressure it will automatically inflate another time and try again.
- 3. You can press the blue button again to take extra blood pressure measurements if you are feeling unwell.
- 4. You should fill out the diary. Make a note of the position you are in (sitting, standing, laying).
- 5. Include your medications, meal times and sleep times.

Step 3: Measuring your blood pressure

- The cuff will inflate every 30 minutes to take your blood pressure. The screen may not show your blood pressure readings. The monitor will store your readings in its internal memory.
- When the cuff is inflating, make certain you keep you arm relaxed and still. If the machine cannot measure your blood pressure it will automatically inflate another time and try again.
- 3. You can press the blue button again to take extra blood pressure measurements if you are feeling unwell.
- You should fill out the diary. Make a note of the position you are in (sitting, standing, laying). Include your medications, meal times and sleep times.

Step 3: Ending a recording.

You should arrive at the Center on the morning of your visit still wearing the monitor.

CONFIDENTIAL

CARBIDOPA IN FAMILIAL DYSAUTONOMIA PHASE II STUDY

Version: 5.0 (date February 12, 2018)

CARBIDOPA IN FAMILIAL DYSAUTONOMIA PHASE II STUDY

Version: 5.0 (date February 12, 2018)
